9.4.3 Safety Analyses

All safety analyses will be performed on the Safety Analysis Set.

Adverse Events

Adverse events will be coded using the Medical Dictionary for Regulatory Activities (MedDRA; Version 23.0 or higher). Treatment-emergent adverse events (TEAEs) are AEs with onset or worsening after the start of study treatment. The AE summaries will be primarily based on TEAEs. The number and percentage of subjects with TEAEs will be summarized by treatment group, system organ class, and preferred term for all TEAEs, treatment-related TEAEs, SAEs, serious TEAEs, severe TEAEs, TEAEs of special interest, and all TEAEs leading to study drug discontinuation. All TEAEs will be further summarized by maximum severity and causality. The TEAEs of special interest will be identified in the SAP.

All AEs will be presented in a by-subject listing. Serious AEs, severe AEs, and AEs leading to study discontinuation or death will be presented in separate listings.

Clinical Laboratory Tests

Laboratory data will be summarized using descriptive statistics for each parameter, including change from baseline at each assessment time by treatment group. Frequency tables or shift tables will be used to present the number and percentage of subjects with laboratory values within/outside reference ranges. All laboratory data will be present in the listings. A by-subject listing will also be provided for subjects with abnormal laboratory results.

Electrocardiogram

Descriptive statistics will be used to summarize the observed and change from baseline values of the following ECG parameters at each assessment time by treatment group: heart rate, PR interval, QRS interval, QT interval, and QTcF. All ECG data will be present in listings.

Vital Signs

Vital sign parameters including temperature, pulse/heart rate, respiratory rate, SpO₂, and blood pressure will be summarized descriptively for both the observed and change from baseline values at each assessment time by treatment group. Frequency tabulations will be provided for abnormalities as applicable.

Other Safety Questionnaires and Assessments

All physical examination results will be listed by subject.

Prior and concomitant therapies will be summarized separately and tabulated for each treatment group using frequencies and percentages. Percentages will be based on the number of subjects in each treatment group. Prior and concomitant medications will be listed by subject.

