Table 2 Description of Analysis Sets

Analysis set	Description
Screened Analysis Set	All subjects who signed the informed consent form.
Full Analysis Set (FAS)	
The FAS will consist of all randomized subjects who receive any amount of study treatment and have at least 1 postbaseline assessment available. This population will serve as the basis for efficacy analysis.
 
Subjects will be analyzed according to their randomized treatment.

Safety Analysis Set (SAS)	
The SAS will consist of all randomized subjects who receive any amount of study treatment.
 
This analysis set will be used for all summaries of subject disposition, demographic and baseline data, and safety information including AE incidence.
 
Subjects will be analyzed according to the treatment they actually received.

H. Subgroups of Analysis Populations

Data from subgroups of subjects in the defined analysis populations will be analyzed as specified below. These analyses will comprise descriptive summaries; the goal will be to identify signals of additional effects that analyses of data from the defined populations do not take into account. Such analyses will be considered exploratory and other subgroups may be considered. They may not be sufficient for drawing conclusions; hence, these analyses will not involve hypothesis testing.

- Age Group (18-44, 45-65 years))
- Sex (Male, Female)
- Region (United States or Europe)
- Duration of depression (<5 years, 5-10 years, > 10 years)
- Duration of current episode of depression (weeks)
- Number of previous treatment failures in the current episode (<3, >=3)
- Baseline MADRS Score (<35, ≥35)
- Baseline medication
 - o Selective Serotonin reuptake inhibitor (SSRI)

- o Serotonin and norepinephrine reuptake inhibitor (SNRI)
- o Antidepressant with adjunctive medications

I. Data Display Characteristics

Data displays produced for this study will include three types—summary tables, data listings, and figures. Unless stated otherwise, data listings will be produced for all recorded data. Summary tables will be produced as specified in the following sections. Additional data listings will be produced for outcome measures that involve extensive procedures to derive the analyzed outcomes. Figures will be produced when specified in sections to follow.

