Data listings will simply list the data recorded on the CRF or derived for each subject. They will be ordered by treatment, site, subject number, and time of assessment. When expedient, additional levels of ordering hierarchy may reflect subsets of assessments within subject. Data listings will not display subject initials.

Summary tables will display summary statistics calculated for each of the treatment groups, unless described otherwise in the following sections. Tables may have either of two general layouts. When the greatest interest is in direct comparison of one treatment group with the others at particular times, different columns of a summary table will display the statistics for the different treatment groups.

The summary statistics displayed will be a function of the type of data associated with the summarized assessment. Unless stated otherwise in relevant sections to follow, continuous data will be summarized with the number of non-missing values, arithmetic mean, standard deviation, minimum, quartile 1 (Q1), median, quartile 2 (Q3), and maximum. Categorical data will be summarized with the number of nonmissing values and the numbers of values equal to each of the possible values. Percentages of subjects with each of the possible values will be calculated from the number of subjects in the corresponding analysis population, unless stated otherwise. Some continuous variables may also be grouped into categorical levels and evaluated in frequency tables.

A subset or all of the following tabular column headers will be used in presenting data for the study:

- PCN-101 60 mg
- PCN-101 30 mg
- Placebo

Efficacy analysis will be implemented according to the planned randomization treatment schedule. Safety analysis will be implemented according to the actual dosed treatment.

VI. Subject Accountability

Unless otherwise indicated, the subject characteristics will be presented by treatment groups for the FAS. The same analysis will be repeated for the SAS if the composition of subjects within these analysis sets are different from the FAS.

A. Disposition

Subject disposition events (screened, randomized, completed treatment, completed the study, early discontinuation from the study along with the reason for discontinuation) will be summarized using frequency counts and percentages by treatment groups.

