Endpoint	Main	Sensitivity
Primary: Change from baseline MADRS total score	MMRM (observed cases [OC], FAS)	MMRM (MI, complete cases, and treatment compliant cases, FAS)

Secondary: ≥50% improvement in MADRS total score	Logistic Regression (OC, FAS)	Logistic Regression (MI, complete cases and treatment compliant cases, FAS)
MADRS total score ≤ 10	Logistic Regression (OC, FAS)	Logistic Regression (MI, complete cases and treatment compliant cases, FAS)
Change from baseline in QIDS-SR-16, GAD-7 and EQ-5D-3L	MMRM (OC, FAS)	MMRM (complete cases and treatment compliant cases, FAS)
CGI-S, CGI-I score	MMRM (OC, FAS)	MMRM (complete cases and treatment compliant case, FAS)

K. Exploratory Analyses

All descriptive statistics analyses which are performed on the FAS as detailed in [Section VII Efficacy Analyses](#) for the primary and secondary endpoints will be repeated based on the subgroup categories as detailed in [Section V.H Subgroups of Analysis Populations](#).

L. Pharmacokinetics

Not applicable.

VIII. Safety Analyses

All safety related analyses will be performed on the SAS except for the listings of SAEs and AEs leading to death, which will be presented for the FAS.

A. Treatment Exposure and Compliance

Study treatment non-compliance is defined as having an infusion duration with a deviation of more than 5 minutes from the 40 minute infusion time (ie, <35 or >45 minutes of infusion duration).

Exposure to PCN-101 or Placebo will be summarized with descriptive statistics for the following exposure measures.

1. Duration of Treatment (minutes)

- If not interrupted, defined as the time of end of infusion – the time of start of infusion+1
- If interrupted, defined as the (time of end of infusion – the time of start of infusion+1) - (infusion restart time – infusion stop time+1)

Details of the infusion drug administration will be listed by subject.

B. Adverse Events

Adverse events (AEs) will be documented on the AE eCRF and monitored continuously throughout the study. Adverse events will be coded using the Medical Dictionary for Regulatory Activities (MedDRA), version 23.0 or higher, associating lower-level terms with preferred terms and system organ classes by the primary hierarchy. All adverse events will be included in the listings.

Treatment-emergent AEs (TEAEs) are defined as AEs that first occurred or worsened in severity after the start of infusion but no later than the second follow-up visit.

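### The SAE and death listings are placed on the FAS, against the protocol's rule that safety outputs use the Safety Analysis Set, so listings and tables may not reconcile

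*SAP*

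**What the plan says.** Protocol 9.4.3 states: "All safety analyses will be performed on the Safety Analysis Set". The same section asks for separate listings of serious AEs and of AEs leading to death, with no other population named for them.

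SAP section VIII follows that rule for safety outputs in general, "except for the listings of SAEs and AEs leading to death, which will be presented for the FAS". It gives no reason for the exception.

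SAP V.G, Table 2, defines the two sets:

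- FAS: "all randomized subjects who receive any amount of study treatment and have at least 1 postbaseline assessment available". On the treatment label: "Subjects will be analyzed according to their randomized treatment".
- SAS: "The SAS will consist of all randomized subjects who receive any amount of study treatment". On the treatment label: "Subjects will be analyzed according to the treatment they actually received".

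SAP V.I adds a general rule for displays: "Safety analysis will be implemented according to the actual dosed treatment". It also makes treatment the first sort key of every data listing.

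SAP VIII.B plans counts and tables of treatment-emergent SAEs, a count of subjects with fatal TEAEs, a listing of all AEs, and the dedicated SAE and death listings. The exception does not name the tables, the counts or the all-AE listing, so these stay on the SAS.

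**The concern.** SAE and death listings are the outputs a reader uses to check that every serious event in a dosed subject has been accounted for. They should draw on the widest set of dosed subjects. Here they draw on a narrower set than the tables they support, and the condition that narrows it, that a subject must "have at least 1 postbaseline assessment available", is most likely to fail in someone who died or was incapacitated soon after the infusion began.

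Two things are at stake. First, completeness and reconciliation: a table could count an SAE or a death that the matching listing does not show. Second, the treatment label: for a subject given the wrong product, the SAP supports two different arms for the same listing.

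**Working it through.** There is no figure in the plan to reproduce. The check is a comparison of the set definitions, then of the outputs.

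**Step 1. Membership, from SAP Table 2, for a randomised subject**

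| Dosed | Post-baseline assessment | In SAS | In FAS |
|---|---|---|---|
| no | no | no | no |
| no | yes | no | no |
| yes | no | yes | no |
| yes | yes | yes | yes |

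The sets differ in the third row only. The FAS is a subset of the SAS, and the only subjects it drops are those dosed with no post-baseline assessment.

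**Step 2. Where such a subject's treatment-emergent fatal SAE would appear**

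| Output (SAP VIII.B) | Set | Shown or counted |
|---|---|---|
| Treatment-emergent SAE tables and counts | SAS | yes |
| Count of subjects with fatal TEAEs | SAS | yes |
| Listing of all AEs | SAS | yes |
| Listing of all SAEs | FAS | no |
| Listing of AEs leading to death | FAS | no |

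The event stays in the report, but the dedicated listings disagree with the tables.

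**Step 3. How wide the gap is**

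The SAP does not say what kind of assessment qualifies a subject for the FAS.

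- *Any assessment counts.* Under the Protocol 1.3 schedule and section 8.0, pulse oximetry and AE review run without a break from before dosing to 4 hours after it. MOAA/S is rated every 20 minutes from the start of infusion. ECG, vital signs, CADSS and BPRS+ follow at the end of infusion. The gap is then confined to the first minutes, or to a subject for whom nothing was recorded.
- *Only an efficacy rating counts.* The FAS is described as the basis for efficacy analysis, so this reading is possible, though not stated. The first post-dose efficacy rating is the MADRS at 2 hours, so the gap would run from the start of infusion to 2 hours. Protocol 7.1 withdraws a subject whose infusion is stopped for an AE. The schedule's footnote on early discontinuation then calls for the Visit 4 procedures, which would usually bring the subject into the FAS, but a fatal or incapacitating event could prevent them.

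Neither reading closes the gap by definition.

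**Step 4. The treatment label**

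For a subject randomised to one arm and given another, Table 2 places an FAS display under the randomised arm. V.I places a safety display under the treatment given. The SAE and death listings are both FAS displays and safety displays, and no rule says which instruction prevails. Because listings are sorted by treatment first, the choice decides where the subject's events are found.

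**The case against.** The strongest case on the other side has four parts.

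*Omission is improbable.* Monitoring is dense from the start of the infusion and the qualifying assessment is unrestricted on its face, so almost any dosed subject will be in the FAS. This stands. A reader might infer that a subject with a serious event during infusion would be missing from both listings; the documents do not support that as a general statement. It needs either no recorded assessment at all or a narrow reading that the SAP does not state.

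*Nothing is lost from the report.* This also stands: the listing of all AEs and the SAS-based tables would hold the event. A reader might express the omission as 1 of 31 in an arm (1/31 = 3.2%). That figure does not apply. A listing has no denominator, and the reported incidence comes from tables that include the subject.

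*The label is not clearly the randomised one.* Correct. A reader might infer from the FAS definition alone that a misdosed subject's SAE would be listed under the wrong treatment. V.I says the opposite, so the documents support a contradiction and no more.

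*Listings are displays, and the protocol's rule concerns analyses.* This does not stand. Protocol 9.4.3 specifies the listings under that same rule, and the SAP itself words its treatment of them as an exception to the safety-analysis rule.

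A reader might also want SAEs before dosing listed for the Screened Analysis Set. That is not needed to cure this defect. It would also first require settling the data source, since Protocol 8.3.1 sends occurrences between consent and the start of treatment to Medical History.

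**Conclusion.** The exception is wrong as written, of minor severity. It contradicts protocol 9.4.3, has no stated purpose, and puts two safety listings on a set that can be smaller than the one behind the corresponding tables. The consequence is a possible failure to reconcile, together with an unresolved treatment label. Affected subjects should be rare; the documents give no number, and if every dosed subject has a post-baseline assessment there are none. No incidence, estimate, power or error rate changes.

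This rests on two assumptions: that the exception reaches only the listings it names, so the all-AE listing and the tables remain on the SAS under the general rule; and that the FAS condition is applied as worded, with the type of assessment left open.

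**What to change.** Delete the exception in SAP VIII, so that the SAE and death listings follow the same rule as the other safety outputs. State that both are presented for the Safety Analysis Set by treatment received, with the randomised arm shown where it differs. This restores agreement with protocol 9.4.3, makes the listings reconcile with the SAS-based tables, and removes the label conflict between Table 2 and V.I for these outputs.

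The cost is one clause of SAP text and a change of population flag and treatment variable in two listing programs. No data collection or other analysis is affected. SAP I.B allows modification up to database lock, so the change can be made in the ordinary way before then.

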6.4 Study Treatment Compliance

The prescribed dosage, timing, and mode of administration may not be changed, except as defined in [Section 6.6](#). Any departures from the intended regimen must be recorded in the appropriate CRFs.

Noncompliance is defined as receiving less than the full infusion or a deviation from the 40-minute infusion time.

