8.4 Treatment of Overdose

An overdose is unlikely during this study since all treatment will be administered in a clinic setting using an infusion pump. However, if the study treatment is administered in less than 40 minutes due to a pump error, the Investigator should:

1. Contact the Medical Monitor immediately.
2. Closely monitor the subject for any AE/SAE and laboratory abnormalities for at least 24 hours.
3. Obtain a plasma sample for pharmacokinetic (PK) analysis as soon as possible and note the time from the start of the infusion of study treatment if requested by the Medical Monitor (determined on a case-by-case basis).
4. Document the quantity of the excess dose as well as the duration of the overdose in the CRF.

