Medical history will be coded using Medical Dictionary for Regulatory Activities (MedDRA) version 23.0 or higher. System Organ Class (SOC) and Preferred Term (PT) will be summarized by number and percentage of subjects having at least one occurrence of the event for the FAS only. All Medical history information be listed by subject.

E. Population Inclusions

A hierarchical table of the populations in which Screened Analysis Set subjects were included will summarize the relationship of the analysis populations. Given population definitions, the Screen Analysis Set will be treated as the parent analysis set. The numbers and percentages of Screened Analysis Set included in the FAS, SAS and PPAS will be presented for each treatment group. The numbers and percentages of FAS subjects included in the SAS and PPAS population will be displayed for each treatment group. This table will be produced for subjects in both US and Europe regions, and as an overall.

VII. Efficacy Analyses

The analysis of the efficacy data obtained from the subjects in this clinical study will be performed on the FAS primarily.

All efficacy analyses will be performed based on a subject's randomized treatment group.

A. Primary Estimand

The primary estimand is defined as follows

- **Population:** Subjects in the FAS and analyzed according to their randomized treatment. The analysis population includes all randomized subjects who receive any amount of study treatment and have at least 1 postbaseline assessment available.
- **Variable:** Change in total MADRS score from baseline at 24 hours after the start of infusion.
- **Intercurrent event:** Incidents where a subject does not receive the full treatment infusion will be considered an intercurrent event. The intercurrent event will however be handled using a treatment policy where all observed values will be used regardless of occurrence of an intercurrent event. No imputation is performed in the primary efficacy analysis.
- **Population-level summary:** Difference in mean change from baseline between each PCN-101 group versus placebo

Additional methodology will be specified for sensitivity and supplementary analyses for assessing the robustness of results. These sensitivity or supplementary analyses will explore different methods for handling intercurrent events and different assumptions for missing data.

B. Primary Efficacy Endpoints

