Sensitivity analyses reviewing missing data assumptions will be performed using the same MMRM model specifications as described in [Section VII.F Primary Efficacy Outcome Analysis](#). One analysis will be performed for only the data collected from subjects who were treatment compliant and a separate analysis will be performed with those who completed the study.

In addition, sensitivity analysis exploring the MAR assumptions with multiple imputation of MADRS related endpoints will be performed as described in [Section VII.E Handling of Missing Item Efficacy Endpoint](#). Analysis of each primary and secondary MADRS endpoints will be performed for each of the MI datasets. The analyzed results from the 50 imputed datasets will be combined based on Rubin's rules (Rubin, 1987) using PROC MIANAYLZE in SAS to estimate the pooled analysis results.

H. Secondary Efficacy Analyses

Change from baseline in MADRS total score

Summaries of actual values and changes from baseline score will be presented by treatment group for all analysis timepoints (including 24 hours after start of infusion), beginning with the Baseline visit for the FAS.

Proportion of subjects with $\geq 50\%$ improvement in MADRS total score

For the responder analysis based on a $\geq 50\%$ improvement in MADRS total score at each analysis visit, the proportion of responders will be calculated using frequency counts and percentages, presented for each treatment group.

The response rate between each PCN-101 dose versus Placebo at each analysis visit will be compared using a logistic regression using fixed effects of treatment group, analysis visit, region and treatment group-by-visit interaction. The baseline value will be included as a covariate. Odds ratios (ORs), corresponding two-sided 95% CI and p--values will be derived.

Proportion of subjects with a MADRS total score ≤ 10

The same analysis will be performed as described for the endpoint of proportion of subjects with $\geq 50\%$ improvement in MADRS total score.

Change from baseline in QIDS-SR-16, GAD-7 and EQ-5D-3L

The MMRM model with the same specification as detailed in Change from baseline in MADRS total score will be used to analyze the following secondary efficacy measures for the FAS. Missing data will not be imputed.

- Change from baseline in QIDS-SR-16 by visit
- Change from baseline in GAD-7 by visit
- Change from baseline in EQ-5D-3L VAS by visit

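### The SAP's duration-only compliance rule omits incomplete infusion, so the treatment-compliant sensitivity analyses exclude the estimand's only intercurrent event incompletely

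*SAP*

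**What the plan says.** **Estimand.** SAP VII.A names one intercurrent event: "Incidents where a subject does not receive the full treatment infusion will be considered an intercurrent event". In the main analysis it is "handled using a treatment policy where all observed values will be used regardless of occurrence of an intercurrent event". The same section says that sensitivity or supplementary analyses will look at other ways of handling intercurrent events, as well as other missing-data assumptions.

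**Compliance in the protocol (6.4).** There are two limbs and no tolerance: "Noncompliance is defined as receiving less than the full infusion or a deviation from the 40-minute infusion time".

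**Compliance in the SAP (VIII.A).** There is one limb, with a tolerance: "Study treatment non-compliance is defined as having an infusion duration with a deviation of more than 5 minutes from the 40 minute infusion time", spelled out as "ie, <35 or >45 minutes of infusion duration". Duration is derived in the same section. The uninterrupted case begins "If not interrupted, defined as the time of end of infusion", then subtracts the start time and adds 1. For an interrupted infusion the pause, also with 1 added, is subtracted.

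**Use of the definition.** SAP VII.G: "One analysis will be performed for only the data collected from subjects who were treatment compliant". A separate analysis covers study completers. Table 3 lists treatment-compliant cases as a sensitivity analysis for the primary endpoint and for each secondary endpoint it shows.

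**The concern.** The limb of protocol 6.4 that the SAP leaves out is the intercurrent event itself. The compliant set is therefore chosen on how long the infusion ran, while the estimand's event is whether all of it was received. The two overlap but are not the same. Some subjects with the event can stay in the compliant set, and some without it can be removed.

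What is at stake is how the sensitivity results are read. If the compliant-subject estimate agrees with the main one, a reader may take this as evidence that incomplete infusions do not drive the result. That inference is sound only if the compliant set is free of incomplete infusions. The SAP's statement that other handling of intercurrent events will be explored depends on some analysis doing this properly.

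**Working it through.** **Inputs.** The planned infusion is 40 minutes (protocol 4.1 and Table 2). The window and duration formulas are in SAP VIII.A, and the intercurrent event is in SAP VII.A. *Assumption:* the pump runs at a constant rate and delivers the whole dose in 40 minutes; the documents give no rate profile.

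**1. The stated window.** 40 − 5 = 35 and 40 + 5 = 45, which matches the SAP.

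**2. Uninterrupted infusion stopped early at *m* elapsed minutes.** SAP duration = *m* + 1. Undelivered share = (40 − *m*)/40. Every row is an intercurrent event.

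| Stop (elapsed min) | SAP duration | SAP status | Dose undelivered |
|---|---|---|---|
| 10 | 11 | non-compliant | 75% |
| 20 | 21 | non-compliant | 50% |
| 30 | 31 | non-compliant | 25% |
| 33 | 34 | non-compliant | 17.5% |
| 34 | 35 | compliant | 15% |
| 36 | 37 | compliant | 10% |
| 39 | 40 | compliant | 2.5% |

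The rule removes the larger losses and keeps stops from 34 to just under 40 minutes. Without the added minute, the cut would be 35 minutes, with (40 − 35)/40 = 12.5% undelivered.

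**3. One interruption.** Start 0, pause at 20, restart at 30, end at 45: (45 − 0 + 1) − (30 − 20 + 1) = 46 − 11 = 35, so compliant. The added minutes cancel. Net infusion is 35 minutes, or 35/40 = 87.5% of the dose. Ending at 44 gives 34, non-compliant.

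**4. Incomplete dose over a normal duration** (for example a slow pump or lost volume). The rule has no volume component, so the subject is compliant whatever the shortfall. The 15% bound in step 2 does not apply here.

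**5. Complete infusion outside the window.** A full dose in 33 elapsed minutes gives 33 + 1 = 34, excluded. One in 44 gives 45, kept. One in 45 gives 46, excluded. None of these is an intercurrent event. Protocol section 8 foresees infusions that run past 40 minutes.

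**6. Could another planned analysis serve instead?**
- Multiple imputation, and the missing-not-at-random analyses triggered by more than 5% missing at 24 hours (SAP VII.E), concern missing scores.
- The completer analysis removes subjects whose infusion was stopped for an adverse event, because protocol 7.1 withdraws them. Protocol 7.1 states no such withdrawal for other stops, and the completer set also loses subjects who leave for unrelated reasons up to Day 15.
- A per-protocol set is mentioned in SAP VI.E but is not defined in SAP Table 2.

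**7. Scale.** One subject is 1/31 = 3.2% of a planned arm. The documents give no expected number of intercurrent events, so no shift in an estimate can be calculated. The stated 80% power (31 per arm, 8 points, SD 11, two-sided 0.05) recomputes to 80.4% by t-test and does not depend on the compliance rule.

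**The case against.** The strongest reply is that the rule already removes the incomplete infusions that matter most. A short infusion has a short duration, and every uninterrupted stop up to 33 elapsed minutes falls outside the window. This stands. A reader might infer that the compliant analysis fails to exclude the intercurrent event at all; step 2 of the working shows otherwise.

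A second reply is that SAP VII.G introduces the compliant analysis as a review of missing-data assumptions and does not name the intercurrent event. This also stands: the link comes only from the general statement in VII.A. But if the compliant analysis was never intended for the event, no listed analysis targets it and that statement has nothing behind it. The SAP needs the correction on either reading.

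Third, a reader might infer that the compliant analysis is the only one that touches the event. It is not, because the completer analysis removes the stops due to adverse events. What remains true is that no planned analysis isolates the event.

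Fourth, excluding a full dose given over 46 minutes agrees with protocol 6.4, which counts a timing deviation as noncompliance. That is correct. Such exclusions blur the view of the intercurrent event but do not depart from the protocol, so the duration limb should stay. Since 6.4 read literally has no tolerance, some tolerance in the SAP is a reasonable way to apply it.

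Finally, a reader might see a contradiction between the 2-minute window in protocol section 8, the protocol 8.4 instruction that applies "if the study treatment is administered in less than 40 minutes due to a pump error", and the SAP's 5 minutes. The documents do not support this. The first concerns the timing of end-of-infusion procedures, the second the actions after a pump error, and the third the classification of subjects for analysis.

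**Conclusion.** The point holds as a mismatch between SAP VIII.A, protocol 6.4 and the estimand. The treatment-compliant sets exclude the sole intercurrent event incompletely and also drop some subjects who did not have it, so the aim in SAP VII.A of exploring other handling of intercurrent events is not properly met.

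For uninterrupted early stops, the retained cases have missed at most 15% of the dose, given a constant rate and the SAP's added minute. For incomplete doses over a normal duration there is no such bound. The primary estimate is untouched because it uses all observed values under treatment policy, and power is unchanged. The effect on the sensitivity estimates is probably small, but this is a judgement, since the frequency of the event is not given. The infusion details listed by subject under VIII.A may make individual cases visible, but they would not correct the analysis sets.

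**What to change.** Before unblinding:

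1. Add a second limb to the SAP VIII.A definition, so that a subject who did not receive the whole infusion is non-compliant whatever its duration. This restores both limbs of protocol 6.4.
2. State that the 5-minute window is the tolerance applied to the duration limb.
3. Refer to this definition in SAP VII.G and Table 3.
4. Report, by arm, subjects excluded for an incomplete infusion separately from those excluded for duration only, so that the effect of the intercurrent event can be seen.

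Under the revised rule every early stop before the full infusion is excluded, including the band from 34 to just under 40 minutes.

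**Cost.** This is a wording change and one extra row or footnote in a table. SAP I.B allows changes until database lock, and protocol 6.4 already requires departures from the regimen to be recorded in the CRF. The documents do not show a specific field for full infusion received, so the sponsor should confirm that the infusion record supports a yes/no classification. The blinded deviation review in SAP VI.B is a natural place to settle it. No change to sample size or to the primary analysis is needed.
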